4.7 Schedule of Events

	Screening (-30 to -1 Days)	Day 0	Day 30	Day 60	Day 90	Day 120	Day 150	Day 180	Day 210	Day 240	Day 270	Day 300	Day 330	Day 360	Day 480	Day 600	Day 720
			(Window +/- 7 days)														
			M1	M2	M3	M4	M5	M6	M7	M8	M9	M10	M11	M12	M16	M20	M24
Consent	X																
Complete Medical History	X																
Interval Medical History		X	X	X	X	X	X	X	X	X	X	X	X	X	X	X	X
Physical Examination	X	X			X			X			X			X	X	X	X
Skin Assessment (including pictures)	X	X	X	X	X	X	X	X	X	X	X	X	X	X	X	X	X
Alcohol & Tobacco use questionnaires	X																
Adverse Event/SAE Review														Each visit			
Urine Pregnancy	X																
Anti-HCV antibodies	X																
PTT	X																
Hepatitis B Surface Antigen	X																
HIV-1/HIV-2 Antibodies	X																
Serum Ferritin	X																
Serum iron and TIBC	X																
Complete Metabolic Panel\$	X	X	X	X	X	X	X	X	X	X	X	X	X	X	X	X	X
INR**	X																
HbA1c	X																
Erythrocyte UROD enzyme activity*	X																
UROD mutation analysis*	X																
HFE genetic testing*	X																
Hematology with Differential#	X	X	X	X	X	[X]*	[X]*	X	X	X	X	X	X	X	X	X	X
HCV RNA	X	X				[X]*	[X]*	[X]									
Plasma Total Porphyrins	X	X	X	X	X	X	X	X	X	X	X	X	X	X	X	X	X
Spot Urine ALA, PBG, Total Porphyrins	X	X	X	X	X	X	X	X	X	X	X	X	X	X	X	X	X
Fibroscan (if available at institution)	X														X		X
Dispense Study Drug [€]		X	X	X	X	X	X	X	X								

Hematology (complete blood count): white blood cell count (WBC), red blood cell count (RBC), hemoglobin, hematocrit, platelet count

\$Comprehensive metabolic panel: sodium, potassium, chloride, carbon dioxide, calcium, BUN, creatinine, glucose, and liver panel, including total protein, albumin, total bilirubin (TBR), alanine aminotransferase (ALT), aspartate aminotransferase (AST), alkaline phosphatase (AP)

*If not previously done

**INR (if not done within 4 months of screening)

[€]Drug is only to be dispensed at months 2-6 if additional therapy is warranted

[X]* Samples at these time points will be obtained only in subjects with cirrhosis who 24 weeks of Harvoni therapy is indicated; [X] Samples at these time points will be obtained 3, 6, and 12 months after the end of Harvoni treatment, and annually till end of study or EOT

4.8 Investigational Product

All study drug will be stored and dispensed from individual centers' research pharmacies according to their standard operating procedures. Drug will only be dispensed after authorized by a site Investigator and to a member of the study team. All study drug will be provided to each site by Gilead Sciences, Inc. through communication with Wake Forest University School of Medicine.

Obtaining Study Drug: Once a potential participant is identified, the site will contact the project manager at Wake Forest University School of Medicine to have study drug sent to the research pharmacy at the site to be dispensed to the study team and the patient.

Dispensing, Dosage, and Accountability: All participants will receive treatment for either 8, 12, or 24 weeks depending upon the usual clinical criteria and recommendations that inform clinical treatment of HCV with Harvoni: We anticipate that, for most subjects, the duration of indicated treatment will be 12 weeks. For patients with cirrhosis, previously treated for HCV infection without response or with response followed by relapse, the duration of treatment will be 24 weeks. Study drug will be dispensed with 4 week supplies (28 tablets). It is recommended that 1 week of additional drug is provided, in case of the need for follow-up appointments to be rescheduled. New supplies of drug will not be provided to subjects until the previous supply has been accounted for by the site coordinator or investigational pharmacy and reconciled. Medication will only be provided at in person study visits, no medication will be mailed to subjects.

The dosage is one tablet of the combination of ledipasvir (90 mg) + sofosbuvir (400 mg) taken daily with or without food. Tablets should not be broken or chewed. No dose adjustments are recommended based upon considerations of age, mild or moderate renal impairment, or mild, moderate, or severe hepatic impairment.

At each study visit the participant will bring all study drug with him or her. The site coordinator will count and reconcile all study medication at each visit. At each visit the subject will return all previous study drug and empty bottles and receive a new 4 week supply. At the final treatment visit (8, 12, or 24 weeks, as may be appropriate), a new supply will not be issued.

Study Drug Destruction: Medication returned by subjects can be destroyed onsite per institutional SOP.

5.0 Data and Safety Monitoring Plan

The study protocol will be reviewed and approved by the National Institutes of Health (NIH) and the Data Safety Monitoring Board (DSMB) before submission to CIRB for approval. Participant enrollment may only begin with CIRB approved consent forms.

This is an interventional study that meets the federal definition of moderate risk.

5.1 Study Oversight

The Study Chair has primary oversight responsibility of this clinical trial. The NIH appointed Data (Observational) Safety Monitoring Board (D/OSMB) has oversight responsibility of the Data Safety Monitoring Plan (DSMP) for this clinical trial. The D/OSMB will review accrual, patterns and frequencies of all adverse events, and protocol compliance every 6 months. The D/OSMB makes recommendations to the NIH regarding the continuation status of the protocol.

Each site's Principal Investigator and his/her research team (co-Investigators, research nurses, clinical trial coordinators, and data managers) are responsible for identifying adverse events. Aggregate reports- detailed by severity, attribution (expected or unexpected), and relationship to the study drug/study procedures – will be available from the DMCC for DSMB review. Adverse events will be reviewed at each study visit by the research team. A separate report detailing protocol compliance will also be available from the DMCC for DSMB review. The research team will then evaluate whether the protocol or informed consent document requires revision based on the reports.

5.2 Definitions and Standards

The Rare Diseases Clinical Research Network defines an adverse event as: "...an unfavorable and unintended sign, symptom or disease associated with a participant's participation in a Rare Diseases Clinical Research Network study."

Serious adverse events include those events that "result in death; are life-threatening; require inpatient hospitalization or prolongation of existing hospitalization; create persistent or significant disability/incapacity, or a congenital anomaly/birth defects."

An unexpected adverse event is defined as any adverse experience, the specificity or severity of which is not consistent with the risks or information described in the protocol.

Expected adverse events are those that are identified in the research protocol as having been previously associated with or having the potential to arise as a consequence of participation in the study.

All reported adverse events will be classified using the current version of the Common Terminology Criteria for Adverse Events (CTCAE) developed and maintained by CTEP at the National Cancer Institute.

5.3 Expected/Known Risks/Discomforts/Adverse Events Associated with Study Intervention and Procedures: Definition of Expected Adverse Events

Drug Information for Harvoni

It was determined by the Food and Drug Administration that this study does not require an Investigational New Drug application.

Human Toxicity/ Adverse Events (adapted from package insert dated March 2015) The safety assessment of HARVONI was based on pooled data from three Phase 3 clinical trials of subjects with genotype 1 chronic hepatitis C (CHC) with compensated liver disease (with and without cirrhosis) including 215, 539, and 326 subjects who received HARVONI for 8, 12 and 24 weeks, respectively.

The proportion of subjects who permanently discontinued treatment due to adverse events was 0%, <1%, and 1% for subjects receiving HARVONI for 8, 12, and 24 weeks, respectively.

The most common adverse reactions ($\geq 10\%$) were fatigue and headache in subjects treated with 8, 12 or 24 weeks of HARVONI.

Table 2 lists adverse reactions (adverse events assessed as causally related by the investigator, all grades) observed in $\geq 5\%$ of subjects receiving 8, 12, or 24 weeks treatment with HARVONI in clinical trials. The majority of adverse reactions presented in Table 2 occurred at severity of grade 1. The side-by-side tabulation is to simplify presentation; direct comparison across trials should not be made due to differing trial designs.

Table 2 Adverse Reactions (All Grades) Reported in $\geq 5\%$ of Subjects Receiving 8, 12, or 24 Weeks of Treatment with HARVONI

	HARVONI 8 weeks N=215	HARVONI 12 weeks N=539	HARVONI 24 weeks N=326
Fatigue	16%	13%	18%
Headache	11%	14%	17%
Nausea	6%	7%	9%
Diarrhea	4%	3%	7%
Insomnia	3%	5%	6%

Laboratory Abnormalities:

Bilirubin Elevations: Bilirubin elevations of greater than $1.5 \times \text{ULN}$ were observed in 3%, <1% and 2% of subjects treated with HARVONI for 8, 12, and 24 weeks, respectively.

Lipase Elevations: Transient, asymptomatic lipase elevations of greater than $3 \times \text{ULN}$ were observed in <1%, 2%, and 3% of subjects treated with HARVONI for 8, 12, and 24 weeks, respectively.

Creatine Kinase: creatine kinase was not assessed in Phase 3 trials of HARVONI. Isolated, asymptomatic creatine kinase elevations (Grade 3 or 4) have been previously reported in subjects treated with sofosbuvir in combination with ribavirin or peginterferon/ribavirin in other clinical trials.

Study Procedures:

Venipuncture: The vein in which the needle has been inserted to draw blood may become sore and red. A temporary “black and blue mark” may develop, and rarely fainting may occur.

Safety Endpoints

Grade 3 or 4 toxicities: According to the scale of the World Health Organization. For liver tests, total serum bilirubin greater than 2.5 mg/dL or, if elevated at baseline, more than at 3-fold increase above the baseline level; serum ALT or AST or AP greater than 3 x ULN, or if elevated at baseline, > 3 x baseline level; INR > 2.0.

Worsening PCT symptoms: PCT is a rare disease and no standard disease severity scale exists. A standardized detailed skin assessment including pictures will be done at each time point in this study. If a subject experience significantly worsening symptoms in the opinion of the investigator that persist for 60 days, HCV therapy will be discontinued under the study and standard of care PCT treatment will be initiated. This length of time may be shortened depending on the severity of the subject’s PCT symptoms. Any patient who experiences worsening PCT symptoms must be discussed by the site PI with the Study Chair prior to discontinuing Harvoni.

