4.2 Exclusion Criteria

1. Women who are pregnant or who are breast-feeding
2. Patients who have already started treatment of PCT with phlebotomy or low dose hydroxychloroquine or chloroquine, or who have been in such treatment in the past 30 days
3. Patients who have already started another treatment regimen for CHC, or who have taken such treatment in the past 30 days
4. HIV infection with CD4 counts at baseline less than 350/ μ L or with evidence of any active AIDS-defining illnesses
5. Ongoing active alcohol abuse, defined as a history of drinking more than 25 drinks of alcohol per week during most weeks in the prior 4 months (History of prior, but not current alcohol abuse will NOT be grounds for exclusion because we seek to treat subjects with PCT and CHC of the type typically seen in clinical practice)
6. Any ongoing active IV drug use
7. Patients who are taking Amiodarone or who have taken Amiodarone within 60 days prior to enrollment
8. Patients who are taking, or within the prior 28 days have taken, rifampicin or St John's wort (*Hypericum perforatum*), both of which are P-gp inducers, which may significantly reduce the drug levels and therapeutic effects of Harvoni
9. Uncontrolled diabetes (Hgb A1c $>9.5\%$ within 60 days prior to enrollment)
10. Chronic hepatitis B
11. Autoimmune hepatic liver injury—autoimmune hepatitis, primary biliary cholangitis/sclerosing cholangitis or overlap syndrome
12. Alcoholic hepatitis

13. Other metabolic disorders of the liver, e.g. Alpha 1 antitrypsin deficiency with ZZ Pi type, Wilson's disease
14. Prior known or suspected drug-induced liver injury within 6 months of enrollment
15. Known or suspected hepatocellular carcinoma
16. On liver transplant list, or current MELD >12
17. History of liver transplant
18. Estimated GFR (creatinine clearance) <30 mL/min (per Sofosbuvir being cleared by the kidney)
19. Serum ALT or AST >10x upper limit of normal
20. Serum bilirubin >2 mg/dL (excluding patients with known or suspected Gilbert's syndrome)
21. Any other comorbid condition, which in the opinion of the investigator precludes participation
22. Incarcerated individuals

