4.5 Data Elements

The following laboratory tests and procedures will be used as the primary data elements:

- Medical history
- Physical examination

- Photographs of areas with PCT skin lesions
- Spot plasma and urinary porphyrins (including HPLC), and urinary creatinine concentrations
- Alcohol Consumption Questionnaire will assess alcohol use
- Serum HCV RNA by PCR
- Anti-HCV antibodies
- Complete metabolic panel (CMP), which includes:
 - Liver chemistries (serum ALT, AST, total bilirubin, albumin, total protein)
 - Serum creatinine, sodium, potassium, chloride, carbon dioxide, calcium, BUN, glucose
- CBC with differential
- INR
- Serum iron and TIBC
- Serum ferritin

These will be completed per the 4.7 Schedule of Events Flow Chart. In addition there will be adverse events reviewed at each visit.

If liver biopsies and/or Fibroscans have been performed, as part of standard of care, results of these will be entered into the study data CRF's; however, no liver biopsies or Fibroscans will be required for inclusion.

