4.6 Study Procedures

Screening and Enrollment:

Potential subjects will be invited to take part and to sign informed consent forms. All participating centers will obtain CIRB approval.

Data collected at baseline will include demographic and clinical information. The screening laboratory tests will be:

- Serum HCV RNA by PCR (obtained within 30 days of enrollment)
- Anti-HCV antibodies
- CMP
- CBC with differential
- INR (if not done within 4 months of screening date)
- PTT
- Hepatitis B surface antigen
- Hemoglobin (Hgb) A1c
- Antibodies to HIV (if not done within 4 months of screening date). Those found positive will undergo HIV RNA and CD4 counts, to assure immune competence. Subjects with known HIV infection, with CD4 counts > 350/ μ L, whether receiving anti-HIV therapy or not, will **not** be excluded unless they require continuation of drug(s) contraindicated in subjects to receive Harvoni

- Spot plasma total porphyrins
- Spot urine delta-aminolevulinic acid (ALA), porphobilinogen (PBG), total porphyrins (including HPLC), and creatinine concentrations
- UROD enzyme activity and mutation analysis, if not previously done
- Serum iron and TIBC
- Serum Ferritin
- *HFE* genetic testing for C282Y and H63D, if not previously done
- Documentation of PCT symptoms and photographs of affected regions (hands, forearms, etc.)
- Alcohol and Tobacco use questionnaires
- Urine pregnancy for females of child-bearing potential

At baseline/screening, following informed consent, a standard interview to assess history of past and current alcohol use. HCV genotype should be confirmed prior to the screening visit as standard of care. History of smoking and current smoking status will also be assessed by interview and results recorded in suitable case report forms (CRFs). All prescription or over-the-counter drugs, including herbals, botanicals, and 'supplements' currently being taken or taken within the two weeks prior to screening, will be recorded, to include name, daily dose, and approximate duration of therapy (estimated to nearest month and year). Particular inquiry will be made regarding any and all estrogen use, including phyto-estrogens, as may be found in herbals and dietary supplements, such as black cohosh. All subjects will be evaluated by a hepatologist (the site PI or a Co-I) at baseline for liver disease based on the criteria detailed above for inclusion/exclusion.

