The therapy will be Harvoni at the usual dose (90 mg of ledipasvir and 400 mg of sofosbuvir) and duration for CHC therapy. One tablet taken daily for 8 weeks for patients without cirrhosis, not previously treated with HCV GT1 and HCV RNA < 6 million IU/mL; 12 or 24 weeks, duration to be determined based upon clinical features and prior treatment experience. 8 or 12 weeks for subjects with or without cirrhosis, not previously treated with anti-virals for CHC, and 24 weeks for subjects with cirrhosis who were previously treated with anti-virals for CHC without having achieved SVR. During the first year study visits will be monthly, and this includes the treatment period of either 12 or 24 weeks. To assess cure of HCV infection, repeated HCV RNA levels at 3, 6, and 12 months after end of Harvoni therapy will be done, as well as annually thereafter. Evaluation by a hepatologist at follow up visits will be as needed, determined by the screening lab test results and by clinical and lab findings at follow-up visits.

Lab measures to be checked monthly during therapy will include CBC, CMP, plasma total porphyrins, urinary total porphyrins (with HPLC), and levels of HCV RNA in serum by quantitative PCR (Section 4.7 Schedule of Events).

Porphyrin specific lab tests will be performed at the UTMB Porphyria Laboratory; all other labs will be performed at Covance Laboratories.

Subjects who have their treatment discontinued for any reason will continue to be followed until the end of the study, including longer-term follow up visits, unless they withdraw consent. If a subject becomes pregnant during the study Harvoni will be discontinued. The outcome of the pregnancy will not be followed as part of this study. Pregnancy during the study should be reported as an SAE.

Longer-Term Follow-up:

12 months after beginning treatment, subjects will be asked to return every four months for one year, with repeat of interval history and physical examination (especially to reassess the status of cutaneous lesions of PCT) and the above studies.

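### INR > 2.0 is a listed liver safety endpoint, but no INR is scheduled at any of the 16 visits from Day 0 to Day 720

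*Combined protocol and SAP*

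**What the plan says.** Section 5.3, under Safety Endpoints, sets liver criteria within the Grade 3 or 4 toxicities. They cover bilirubin, ALT, AST and AP, and the list closes with "if elevated at baseline, > 3 x baseline level; INR > 2.0".

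The timing of INR is set elsewhere:

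- **Section 4.5** names INR as a data element and leaves timing to the schedule: "These will be completed per the 4.7 Schedule of Events Flow Chart".
- **Section 4.6, screening tests**, lists it conditionally: "INR (if not done within 4 months of screening date".
- **Section 4.7** marks INR once, in the screening column, with a footnote repeating the condition: "INR (if not done within 4 months of screening".
- **Section 4.6, treatment visits**, begins the monthly list with "Lab measures to be checked monthly during therapy will include CBC, CMP, plasma total porphyrins" and goes on to urinary porphyrins and HCV RNA. INR is not named.

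The metabolic panel is marked at screening and at every later visit. Its footnote in 4.7 includes total bilirubin, ALT, AST and AP, but not INR.

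Section 4.6 also provides for hepatologist evaluation during follow-up "as needed, determined by the screening lab test results and by clinical and lab findings at follow-up visits".

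**The concern.** Of the five liver tests in 5.3, INR is the only one the plan does not schedule once the drug is started. Sites that follow the protocol exactly will find an INR above 2.0 only if a clinician happens to order the test. For-cause testing of that kind does not ascertain an endpoint uniformly across patients or sites.

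Two things are at stake. First, Section 5.1 has the monitoring board review adverse event patterns and frequencies every six months. With no scheduled test, zero INR events cannot be told apart from zero measurements. Second, the criterion may bear on treatment. Section 5.3 places it under Grade 3 or 4 toxicities, and 5.7 stops Harvoni for Grade 4 toxicities. Section 5.3 does not say which grade an INR above 2.0 is, so this link is possible but not established.

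Patients with compensated cirrhosis are eligible and may receive up to 24 weeks of drug. The exclusions that limit hepatic risk ("On liver transplant list, or current MELD >12" and "Serum bilirubin >2 mg/dL") apply at entry and do not monitor anyone afterwards.

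**Working it through.** The plan gives no figure to reproduce here. The check is a count of the 4.7 schedule, read against the text of 4.5, 4.6 and 5.3.

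**Visits after screening.** Day 0 to Day 360 in 30-day steps gives 13 visits. Days 480, 600 and 720 add 3. Total 13 + 3 = 16. Drug is first dispensed on Day 0, so 15 of these follow the start of treatment.

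**Scheduled measurements from Day 0 to Day 720**

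| 5.3 liver criterion | Carried by | Visits scheduled |
|---|---|---|
| Total bilirubin | Metabolic panel | 16 of 16 |
| ALT | Metabolic panel | 16 of 16 |
| AST | Metabolic panel | 16 of 16 |
| AP | Metabolic panel | 16 of 16 |
| INR | Own row, screening only | 0 of 16 |

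For 49 patients completing all visits: 49 × 16 = 784 panels, against 0 INRs.

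**Could this be a table-reading error?** No. The 4.7 footnote and the 4.6 screening list both tie INR to screening, and the 4.6 monthly list omits it. PTT is also screening-only, so no coagulation test of any kind is scheduled after treatment starts.

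**How old can the latest available INR be?** Inputs are the four-month waiver (taken as 120 days) and the 30-day screening window in 4.7. This is the oldest value allowed, not a typical one; a waived draw means relying on a historical result.

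- Day 0: 120 + 30 = 150 days
- End-of-treatment visit, 8 weeks (Day 60): 150 + 60 = 210 days
- End-of-treatment visit, 12 weeks (Day 90): 150 + 90 = 240 days
- End-of-treatment visit, 24 weeks (Day 180): 150 + 180 = 330 days

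**Visits at which INR would inform treatment.** Treatment ends at about Day 56, 84 or 168 (8, 12 or 24 × 7).

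| Duration | During treatment, after Day 0 | End-of-treatment visit | Sum | With Day 0 | × 49 |
|---|---|---|---|---|---|
| 8 weeks | Day 30 (1) | Month 2 (1) | 2 | 3 | 147 |
| 12 weeks | Days 30, 60 (2) | Month 3 (1) | 3 | 4 | 196 |
| 24 weeks | Days 30–150 (5) | Month 6 (1) | 6 | 7 | 343 |

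With the ±7-day window, Month 6 spans Days 173–187, so for 24 weeks the end-of-treatment visit always falls at least 5 days after Day 168.

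**The case against.** The schedule count is not in dispute. The case against concerns its importance and the remedy.

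- **The denominator overstates the gap.** Most of the 16 visits come after treatment. On the remedy's own terms the relevant gap is 0 of 3, 0 of 4 or 0 of 7 visits. This is fair, and those are the better figures for judging consequence. The count is still zero on any of them.
- **The age figures stack worst cases.** They do: longest waiver plus earliest screening day. In addition, MELD is conventionally computed from INR, so the MELD exclusion should in practice call for a reasonably recent value at entry. The plan does not define how current it must be, and none of this supplies an INR during treatment.
- **No action is attached to INR > 2.0.** Correct. The link to the Grade 4 stopping rule is an inference, because no grade is given.
- **Other safeguards exist.** The liver panel, including albumin, and adverse event review take place at every visit. Abnormal findings can prompt a hepatologist evaluation, and higher-risk patients are excluded. This limits the harm, but none of these steps requires an INR.
- **A cheaper remedy is possible.** INR could be triggered by another abnormal liver test, or limited to patients with cirrhosis. Either would give the criterion a defined route at lower cost. A triggered test would still miss an isolated INR rise, and a cirrhosis-only rule would leave the endpoint unmeasured in everyone else.

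**Conclusion.** The concern holds. A stated safety endpoint has no scheduled measurement after screening: 0 of 16 visits, or 0 of 4 at the visits that matter for the anticipated 12-week course. The other four liver tests are measured at 16 of 16.

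The consequence is confined to safety ascertainment. The primary endpoint, the decision rule and the analyses in Section 6 are unaffected. The documents give no INR event rate and none is assumed, so the number of events that might be missed cannot be estimated. The change is worth making because it is cheap and removes an inconsistency between 5.3 and the schedule; the trial's conclusion on efficacy does not depend on it.

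The conclusion rests on reading 4.7 as the governing schedule, as 4.5 directs. The reference in 4.6 to repeating earlier studies in longer-term follow-up does not name INR, and 4.7 shows none at those visits.

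**What to change.** Amend 4.6 and 4.7 to add INR at:

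- Day 0, for all patients;
- Month 1, and Month 2 as end of treatment, for 8 weeks;
- Months 1–2, and Month 3 as end of treatment, for 12 weeks;
- Months 1–5, and Month 6 as end of treatment, for 24 weeks.

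Keep the INR threshold in 5.3, since it also classifies an INR obtained for cause, and state its grade so that its relation to the stopping rule in 5.7 is clear. For patients already treated without INRs, report how many were tested and do not present an absence of events as evidence of safety.

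The cost is the assays tabulated above, at blood draws already scheduled, plus one protocol amendment with central IRB approval. The totals of 147, 196 and 343 are ceilings. This version is dated 5 May 2020, about 33 months after activation on 4 August 2017, against a three-year enrolment target. Fewer patients are therefore likely to be affected, although the documents do not say how many remain.
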